### Attribution

Attribution is the relationship between an event and the treatment. Attribution is assigned as follows:

- Definite – The event is clearly related to the study treatment
- Unrelated – There is no reasonable possibility that there is a causal relationship between the study medication and the AE

### Adverse Event Monitoring

Medical history adverse events are recorded and graded using Common Terminology Criteria for Adverse Events (CTCAE) version 5.0. Serious adverse event and adverse event monitoring begins after initiation of study treatment and continues until the Day 60 safety follow up.

Adverse event data collection and reporting are a part of every clinical trial and are done to ensure the safety of participants enrolled in the studies as well as those who will enroll in future studies using similar agents.

Adverse events should be evaluated to determine

- Start and end dates
- Severity or grade
- Seriousness
- Relationship to study agent
- Action taken (i.e., dose held, dose reduced, medical intervention)
- Outcome (i.e., resolved without sequelae, resolved with sequelae, ongoing)

Participants experiencing an adverse event, regardless of its relationship to study drug will be monitored until:

- Adverse event resolves or the symptoms or signs that constitute the adverse event return to baseline.
- Clinically significant abnormal laboratory values have returned to baseline.
- The treating investigator has determined there is a satisfactory explanation other than the study drug for the changes observed.
- Death

The following laboratory abnormalities should be documented and reported as adverse events.

- Meets the definition of an SAE.
- Requires medical intervention (i.e., dose modification and/or other intervention such as supportive medication administration, supplementation, physical therapy, diet change, fluid administration, transfusion, additional testing, etc.)

**Sponsor/Investigator Reporting to FDA**

The University of Kansas Medical Center's Sponsor/Investigator as holder of the IND will be responsible for all communication with the FDA. The Sponsor/Investigator will report any adverse event that is serious, unexpected and reasonably related (possible, probable, definite) to the study treatment.

The Sponsor/Investigator must report the following Suspected Adverse Events as outlined below:

Table 11-1

Event	Report To	Time Frame
Unexpected fatal or life-threatening SAR	FDA	As soon as possible but no later than 7 calendar days after the Sponsor/Investigator's initial receipt of the information.
Any event that is both serious and unexpected SAR	FDA and participating investigators	As soon as possible but no later than 15 calendar days after the Sponsor/Investigator's determine the information qualifies for reporting
Any findings from epidemiological studies, pooled analysis of multiple studies or clinical studies regardless if conducted under an IND or if the Sponsor/Investigator it suggests significant risk to humans exposed to the drug	FDA and participating investigators	As soon as possible but no later than 15 calendar days after the Sponsor/Investigator's determine the information qualifies for reporting
Any findings from animal or in vitro testing, regardless if conducted by the Sponsor/Investigator that suggests a significant risk in humans exposed to the drug	FDA and participating investigators	As soon as possible but no later than 15 calendar days after the Sponsor/Investigator's determine the information qualifies for reporting
Any clinically important increase in the rate of a Serious SAR over that listed in the protocol or Instigator Brochure.	FDA and participating investigators	As soon as possible but no later than 15 calendar days after the Sponsor/Investigator's determine the information qualifies for reporting

Expected SAE's and AE's should be included in the IND Annual Reports.

Follow-up information to a safety report should be submitted as soon as the relevant information is available. However, if the results of the Sponsor/Investigator determines an adverse drug experience not initially determined to be reportable are so reportable the Sponsor/Investigator must report such experience as soon as possible but no later than 15 calendar days after the determination is made.

All other serious unexpected experiences associated with the use of the study treatment will be reported to the FDA as soon as possible but no later than 15 calendar days after initial receipt of the information.

Events will be reported to the FDA by telephone [name] or by fax, [name] using Form FDA 3500 (Voluntary Reporting) for non-IND studies and Form 3500A (Mandatory Reporting) for IND studies.

#### Guidelines for Processing IND Safety Reports

The US Food and Drug Administration (FDA) regulations require Sponsor/Investigators of clinical studies to notify them and all participating investigators of any serious and unexpected adverse experiences that are possibly related to the investigation agent. The Sponsor/Investigator will review all applicable IND Safety Reports and has the responsibility to forward the IND safety reports to the affiliate institutions. The affiliate institution investigators are to review and report to their IRB in accordance with local IRB policies and will file a copy with their regulatory documents.

## APPENDIX B: WHO Ordinal Scale for Clinical Improvement

[figure not shown]
Patient State	Descriptor	Score
Uninfected	No clinical or virologic evidence of infection	0
Ambulatory	No limitation of activities	1
	Limitation of activities	2
Hospitalized, Mild Disease	Hospitalized, no oxygen therapy	3
	Oxygen by mask or nasal prongs	4
Hospitalized, Severe Disease	Non-invasive ventilation or high-flow oxygen	5
	Intubation or mechanical ventilation	6
	Ventilation plus additional organ support – pressors, RRT, ECMO	7
Dead	Death	8

## Appendix C

### **Buccal Mucosa Swab Protocol for Patients:**

This test will be performed on your first and 7th day of the study, both tests being made prior to receiving the study drug. We are collecting two things: 1) cheek-gum cells to look at proteins involved in COVID-19 infection and may predict response to treatment, and 2) cheek-gum cells to look at the DNA to see if there are markers that can predict response to treatment

1. Rinse your mouth prior to performing this procedure (i.e. drinking some water and rinsing it around your mouth is enough)
2. Hold the swab in your hand like you would hold a toothbrush
3. Insert the swab into your mouth so it is resting between your inner cheek and gum ("the gutter"), close your mouth slightly to keep the brush in place
4. Brush vigorously back and forth with the swab for 15-20 seconds making sure the swab stays as far up in your mouth as possible (i.e. **DO NOT** brush your teeth)
5. After 15-20 seconds, open your mouth and carefully remove swab and move it to the next location in your mouth
6. Repeat steps 2-4 ensuring the upper and lower right gutters and upper and lower left gutters are swabbed using the same swab.
7. When finished, carefully remove the swab from your mouth and place into a new small collection vial.

A Trial of Aclaris Therapeutics, Inc. (ATI)-450 in Patients With Moderate-severe Novel Coronavirus Disease 2019 (COVID-19)

Document Date: 3/27/23

Trial Number: NCT04481685

Statistical Analysis Plan

Study Title: A double-blind, randomized, controlled trial of ATI-450 in

patients with moderate-severe COVID-19

Phase: 2A

Protocol No.: IIT-2020-ATI-450-COVID-19

This document describes the statistical methods and data presentations to be used in the summary and analysis of data from Protocol IIT-2020-ATI-450-COVID-19 by the Department of Biostatistics and Data Science of the University of Kansas Medical Center based on the criterion for investigator-initiated trials (IITs) of KUMC.

Study Overview

IIT-2020-ATI-450-COVID-19 is a Phase 2A, double-blinded, randomized, placebo-controlled, proof of concept, safety, efficacy, multi-center study of ATI-450 as monotherapy for treating patients with moderate to severe COVID-19 disease.

Patients who have laboratory-confirmed COVID-19 as determined by polymerase chain reaction (PCR), or other commercial or public health assay in oropharyngeal or nasopharyngeal testing within 14 days of hospitalization, and are currently hospitalized as a result of symptoms and signs related to COVID-19 pneumonia with evidence of hypoxic respiratory failure: pulse oximeter measurement of oxygen saturation (SpO_2) $\leq 93\%$, or $\text{SpO}_2 > 93\%$ requiring $\geq 2\text{L}$ of supplement oxygen (O_2), or partial pressure of oxygen (PaO_2)/ fraction of inspired oxygen (FiO_2) ratio $< 300\text{mmHg}$, or tachypnea (respiratory rate > 30 breaths/min) or evidence of pulmonary involvement by chest imaging or pulmonary exam will be eligible for enrollment into the study. Eligible patients will be randomized in a 1:1 ratio to either 50 mg oral ATI-450 twice daily (BID) or placebo BID for 14 days or until patient discharge whichever is earlier.

Treatment Assignment:

A total of approximately 20 patients will be randomized in a 1:1 ratio:

- Placebo oral tablet BID for 14 days
- ATI-450 oral tablet, 50 mg, BID for 14 days

Survival follow up assessments will be conducted 28-, 45- and 60-Days post hospital Day-1 and all participants should complete these visits. Exceptions include death, lost to follow-up or the participant withdrawing consent for follow-up all of which should be documented in the participants medical record and EDC.

Study objectives

Primary Objective:

The primary objective is to assess the efficacy of ATI-450 on hypoxic respiratory failure-free survival in patients with moderate-severe COVID-19 pneumonia at day 14.

Secondary Objectives:

- To assess the clinical efficacy of ATI-450 on respiratory function and survival in patients with moderate-severe COVID-19 pneumonia.
- To assess the safety of ATI-450 in patients with moderate-severe COVID-19 pneumonia.

Exploratory Objectives:

- To Assess the pharmacodynamics of ATI-450 in patients with moderate-severe COVID-19 pneumonia.

Outcome Measures

Primary Efficacy Measure

- Primary treatment responder: defined as any patient who is alive, free of respiratory failure (does not require supplemental oxygen (greater than pre-existing use)) and does not experience a negative intercurrent event on Day 14 of the trial.

An intercurrent event is one that occurs after the first dose of study medication and either precludes the observation of the primary variable/endpoint or affects its interpretation. The following is a list of negative intercurrent events that could occur during this study:

- Death
- Withdrawal from study
- Intubation and ventilation
- Rescue with a non-protocol specified treatment for cytokine release syndrome

The following is a list of positive intercurrent events that could occur during this study:

- Early hospital discharge due to recovery

A patient will be considered a treatment responder if the primary endpoint is missing following a positive intercurrent event. A patient will be considered a treatment non-responder for all observations (missing or not missing) following a negative intercurrent event.

Secondary Efficacy Measures

- Change from baseline in the WHO COVID-19 7-point ordinal scale over time (**BASELINE, DAY 7, DAY 14, DAY 28**).
- All-cause mortality through Day 60 (**DAY 7, DAY 14, DAY 28 AND FOLLOW-UP**.).
- Responder based on 7-point ordinal scale: Greater than 2-point improvement from baseline on the 7-point ordinal scale. (**BASELINE, DAY 7, DAY 14, DAY 28 AND FOLLOW-UP**.).
- Time to discharge from the hospital.

Safety assessments include:

- Adverse events

Exploratory measures include:

- Change in serum cytokine Interleukin (IL)-6 over time (baseline, d7, EOT, d28).
- Change in serum cytokine IL-8 over time (baseline, d7, EOT, d28).
- Change in serum cytokines IL-1 β over time (baseline, d7, EOT, d28).
- Change in serum cytokine Tumor Necrosis Factor (TNF- α) over time.

*EOT: end of treatment

Sample Size Justification

Data from 20 patients (10 randomized to ATI-450 and 10 to Placebo) provide some preliminary information about the efficacy and safety of ATI-450. No hypothesis will be formally tested. The mean and exact 90% confidence intervals for within-group event rates will be estimated and no between group difference will be estimated.

Randomization and Blinding

Prior to the start of the study, the University of Kansas Medical Center will generate a list of randomization numbers that shall be transmitted to the assigned clinical packaging organization for study medication labeling. The randomization list will be stored with access limited to designated personnel for study medication labeling. The randomization list will be made available, as appropriate, to unblind the database.

In the treatment period, subjects will be assigned to 1 of the 2 treatment groups in a random manner and at a 1:1 ratio stratified by baseline age group (<60 versus \geq 60). At the Day 1 visit an investigational center staff member will assign study medication to eligible subjects by selecting an appropriate Subject Kit. The staff member must select Subject Kits in chronological sequence and in an ascending numerical order starting with the lowest available Subject Kit number. No Subject Kit number may be omitted or reused. The Subject Kit number is the randomization number.

This study uses a double-blind design. The study medications are indistinguishable in appearance, as packaged and labeled.

Analysis populations

- The Full Analysis Set (FAS) will include all patients who have been administered at least one dose of study medication. The FAS will be population used in the primary efficacy analysis. The FAS will also be the population used secondary efficacy analyses and summaries as well as the population used in all safety summaries. The FAS will be analyzed/summarized as randomized when applied to efficacy endpoints. The FAS will be analyzed/summarized as treated when applied to safety endpoints.
- The Per-Protocol population will include all FAS patients who have completed their Day 14 visit and have continued study drug administration through Day 14 or were successfully discharged prior to Day 14. The Per-protocol population will be used for the primary efficacy analysis. Summaries and analyses using the per-protocol population will be done as treated.

Statistical Analysis Methods

Descriptive statistics (number of observations, mean (standard deviation) or median (minimum, maximum)) will be provided for continuous variables, and counts and percentages will be presented for categorical variables for each group.

Primary Efficacy Analysis

The study is hypothesis generating. The primary assessment of efficacy for this study will be the point estimate and corresponding exact 90% confidence interval for the proportions of responders for the ATI-450 and Placebo groups. All subjects who are alive, free of respiratory failure (do not require supplemental oxygen) by Day 14 of the trial will be considered responders. The point estimate and corresponding 90% confidence interval will be derived based on sample proportions and the Copper-Pearson CIs for proportions for the two groups (categorical data analysis by Alan Agresti, 3rd edition).

Secondary Efficacy Analyses

Binary variables will be analyzed using the method like that described for the primary endpoint. In addition to the point estimate and confidence interval for the difference in proportions for binary endpoints, odds ratios, corresponding confidence intervals will be provided. For binary measures that are recorded over time, separate analyses will be conducted at each timepoint.

Continuous secondary efficacy endpoints will be analyzed by estimating group means and mean difference and 95% CIs at each time point. Missing data will be imputed with the single imputation methods described above (LOCF or WOCF).

For time to discharge from hospital, estimates of the median (50th percentile) will be provided for each treatment group and Kaplan-Meier Curves will be provided. A two-sided stratified log-rank test will be applied. The stratification factor will be baseline age group (<60 versus ≥ 60).

Exploratory Outcomes Analyses

For all the Cytokines, changes over time (baseline, d7, EOT, d28) will be summarized by descriptive statistics and trajectory plots. Any time point after the end of treatment (EOT) will not be measured.

Safety Summaries

AEs will be summarized using table format based on DSMB requirements (attached).

Missing Data Imputation

Missing data for binary secondary endpoints will be treated in a similar manner as the primary endpoint. For secondary endpoints of a continuous nature, the last observation prior to the intercurrent event will be carried forward (LOCF) for all positive intercurrent events and the worst observation prior to the intercurrent event will be carried forward (WOCF) for all negative intercurrent events.

Primary efficacy analysis will be done on the Full Analysis Set (FAS) and the per protocol population. Secondary efficacy analyses and safety analysis will be done on FAS only.

The statistical analyses and summaries will be conducted with the SAS® software package version 9.4 or higher.

Attachments:

- *IIT-2020-ATI-450-COVID-19 _DSMB_AdverseEventListingShell.xls*
- *IIT-2020-ATI-450-COVID-19 DSMB ReportTableShells_2020_1008.doc*

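### The SAP replaces the Protocol's primary between-arm difference in Day 14 responders with separate per-arm intervals, does not acknowledge the departure, and conflicts with its own plan for secondary binary endpoints

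*SAP*

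**What the plan says.** **Protocol.** The Protocol Summary and section 15.3 define the primary assessment as the difference in responder proportions, ATI-450 against placebo. It comes with an asymmetric 70% confidence interval from a logistic model containing treatment, age group and gender. Section 15 says more generally that the objectives will be judged by point estimates and intervals.

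**SAP, objective.** The aim is unchanged: "The primary objective is to assess the efficacy of ATI-450 on hypoxic respiratory failure-free survival".

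**SAP, Sample Size Justification.** For 10 patients per arm: "No hypothesis will be formally tested". The next sentence is: "The mean and exact 90% confidence intervals for within-group event rates will be estimated and no between group difference will be estimated".

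**SAP, Primary Efficacy Analysis.** The primary result is the point estimate and "exact 90% confidence interval for the proportions of responders for the ATI-450 and Placebo groups", using Clopper-Pearson limits.

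**SAP, Secondary Efficacy Analyses.** "Binary variables will be analyzed using the method like that described for the primary endpoint". The text continues: "In addition to the point estimate and confidence interval for the difference in proportions for binary endpoints, odds ratios" and their intervals. Continuous endpoints are handled by "estimating group means and mean difference and 95% CIs at each time point". For time to discharge: "A two-sided stratified log-rank test will be applied".

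**The concern.** The two documents name different primary analyses. Quantity estimated, confidence level and method all change, so whichever analysis is run departs from one of them. The SAP neither mentions the Protocol's analysis nor gives a reason for leaving it.

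Randomisation and a placebo arm exist to support a comparison between arms. Two single-arm intervals do not give one, and they invite readers to judge the effect by whether the intervals overlap, which is not a valid substitute for an interval on the difference.

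The SAP is also inconsistent within itself. It rules out between-group differences for event rates, then plans differences and odds ratios for the secondary binary endpoints, which are event rates too (mortality and the ordinal-scale responder). It defines their method by pointing back to the primary analysis. In the Protocol that pointer led to a logistic regression. In the SAP it leads to a one-sample interval, so a programmer would have to choose a method that is not written down.

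**Working it through.** **Step 1. The texts side by side.**

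| Item | Protocol Summary and 15.3 | SAP |
|---|---|---|
| Primary quantity | Difference in responder proportions | Proportion in each arm |
| Level | 70% | 90% |
| Method | Logistic model: treatment, age group, gender | Clopper-Pearson, per arm |
| Secondary binary endpoints | Logistic model as for the primary; difference and odds ratio | As for the primary; difference and odds ratio |

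The last row is consistent in the Protocol. It is not consistent in the SAP, because a Clopper-Pearson interval uses one arm's count and yields neither a difference nor an odds ratio.

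**Step 2. The plan's own precision figure.** The SAP gives none for 10 per arm. Protocol 15.1 states at most 31 points for a 70% interval at 18 per arm with placebo at 50%. The Wald width is 2 × 1.036 × √{[0.5 × 0.5 + p(1 − p)]/18}. With p = 0.5 this is 34.5 points; with p = 0.8 it is 31.3. The Protocol does not state the ATI-450 rate, so the figure can be neither confirmed nor refuted. It is a separate sample-size matter and nothing below rests on it.

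**Step 3. What the SAP would report.** For x responders out of n = 10, the Clopper-Pearson 90% limits are the 5th percentile of Beta(x, n − x + 1) and the 95th percentile of Beta(x + 1, n − x).

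- 5/10: 22.2% to 77.8%
- 7/10: 39.3% to 91.3%
- 8/10: 49.3% to 96.3%
- 9/10: 60.6% to 99.5%

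**Step 4. What it would leave out.** The Miettinen-Nurminen limits are the values d at which (p̂₁ − p̂₂ − d) / √{[p̃₁(1 − p̃₁)/10 + p̃₂(1 − p̃₂)/10] × 20/19} equals ±1.645. Here p̃₁ and p̃₂ are the maximum-likelihood proportions constrained to differ by d.

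| ATI-450 vs placebo | Difference | 90% interval (points) |
|---|---|---|
| 5/10 vs 5/10 | 0 | −35.3 to +35.3 |
| 7/10 vs 5/10 | +20 | −16.6 to +51.9 |
| 8/10 vs 5/10 | +30 | −6.1 to +59.5 |
| 9/10 vs 5/10 | +40 | +5.8 to +66.7 |

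In the last row the per-arm intervals overlap between 60.6% and 77.8%, although the interval for the difference excludes zero. The per-arm display would mislead a reader who judged by overlap.

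**Step 5. Is an interval for the difference workable at 10 per arm?** All 11 × 11 = 121 outcomes were enumerated with placebo at 50% (Protocol 15.1). The ATI-450 rates are assumed, since the documents give none.

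| ATI-450 rate | Coverage at nominal 90% | Expected width (points) |
|---|---|---|
| 50% | 88.4% | 67.8 |
| 60% | 88.7% | 67.3 |
| 70% | 89.1% | 65.6 |
| 80% | 89.5% | 62.4 |
| 90% | 88.5% | 57.4 |

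The interval is wide and covers 0.5 to 1.6 points below nominal, but it can be computed and interpreted.

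**The case against.** **The SAP is entitled to settle details.** The Protocol Summary and section 15 leave statistical details to it. That is true, but removing the treatment contrast from the primary analysis is more than a detail.

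**The reason is obvious.** The sentence stands under the justification for 20 patients, and the Protocol Summary already lists 20 participants. This stands in part: the context is plain. What is missing is an acknowledgement of the departure and a stated reason. A smaller sample widens the interval for a difference; it does not prevent estimating one.

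**It is a pilot.** Protocol 15.3 calls the study hypothesis generating and 15.6 calls it an early pilot, yet the Protocol keeps the difference as primary. The SAP keeps differences for secondary endpoints at the same sample size.

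**Anyone can compute the difference from the counts.** This stands. With two arms and no adjustment no information is lost; the loss is of prespecification and transparency.

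**A reader might infer that the SAP contradicts itself throughout its secondary analyses.** The documents do not support that. The ban can be read as covering event rates only, which leaves the continuous mean differences untouched. A descriptive log-rank test can coexist with an absence of formal testing. The clear conflict is limited to the binary endpoints.

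**A reader might also infer that the Protocol's logistic model cannot be used at 10 per arm.** Simulation does show frequent non-finite coefficients: 5.9% to 46.3% of trials as the ATI-450 rate goes from 50% to 90% with evenly split covariates, and 28.4% to 61.0% with an assumed 20%/35% split. But a non-finite coefficient is not a missing result. The Protocol's target is a difference in proportions, and in roughly 90% or more of such datasets the standardised difference and its delta-method standard error remained finite. Those intervals may perform poorly at this size, but these rates do not rule the model out.

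**Conclusion.** The concern holds. The Protocol's primary difference is dropped, the departure is not acknowledged, and the SAP plans no effect estimate or interval for its primary efficacy objective. The conflict within the SAP is clear for secondary binary endpoints and weak elsewhere.

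The conclusion is textual and depends on no assumed rate. The numbers only show its practical size: a 40-point observed difference would go without its interval of +5.8 to +66.7 points. They also show that a usable interval exists, with an expected width of 57 to 68 points. The widths and coverage assume 10 per arm, placebo at 50% and ATI-450 rates of 50% to 90%.

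The documents do not dictate a particular interval method or level for the restored difference. Miettinen-Nurminen at 90% is one defensible choice. What is needed is a single prespecified choice that both documents share.

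**What to change.** 1. **SAP, Sample Size Justification:** delete the closing clause that rules out a between-group difference.
2. **SAP, Primary Efficacy Analysis:** report as primary the difference in Day 14 responder proportions (ATI-450 minus placebo) with one prespecified interval method and level. Do this in the Full Analysis Set, repeat it in the per-protocol set, and label it estimation only. An unstratified Miettinen-Nurminen 90% interval is one workable option. A standardised difference from the Protocol's age- and gender-adjusted logistic model is another. Keep the per-arm Clopper-Pearson intervals as descriptive.
3. **Protocol Summary and 15.3:** name the same analysis, and state the reason for any change.
4. **SAP, Secondary Efficacy Analyses:** name a two-sample interval method for the difference and for the odds ratio in place of the pointer to the primary method. Label the log-rank p-value descriptive.

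**Cost:** wording in both documents and a few lines of code; no new data. The reported interval will be wide. If the Miettinen-Nurminen option is taken, coverage is slightly below nominal in the cases computed, and the primary estimate loses the age and gender adjustment.
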